9.2 Sample Size Determination

Dose Escalation Part A

The planned cohort size is 3 participants at a given dose. Parallel screening and enrollment of participants will allow eligible participants to enroll, the cohort size may therefore increase to a maximum of 4 participants. Any additional participants enrolled in the study at a given dose, will complete all study procedures and assessments as per protocol and are considered in the Bayesian model if they fulfill the criteria for inclusion in the DLT set.

The total sample size will depend on the number of cohorts and regimens to be evaluated. It is anticipated that 15 to 21 participants (4 projected dose levels with 3 to 9 participants each) may be needed. If change(s) in regimen would occur, the sample size may increase.

The following scenario is anticipated:

2 dose levels with 3 participants each and 2 dose levels with 6 participants each, resulting in 18 participants.

Considering for example one change in regimen after the first dose level, the sample size may increase by 3 if in the new regimen, the above scenario holds.

Dose Expansion Part B

Part B begins with a safety run-in of 6 participants. Dose adjustments during Part B may occur.

Part B will include 30 participants treated at the same dose who are evaluable for response in a two-stage design. This sample size will give a posterior probability of 85% that the ORR \geq 20% if 8/30 responses are seen at the final analysis.

An interim analysis will occur after enrollment of 15 participants treated at the same dose are evaluable for response. The cut-off for the interim analysis was chosen to balance sufficient information for decision with the potential of sparing participants an inefficient treatment. The boundary and operational characteristics are described in Section 9.4.1.

If in the course of the expansion and/or at the interim analysis, the M3258 dose is modified, then only participants treated at the same dose will be considered in the two-stage design. Therefore, the number of participants in the expansion cohort might increase by approximately 3 to 21 participants to reach the required number of 30 participants treated on the same dose who are evaluable for response according to IMWG.

Additionally, in Part B (as well as in Part A) the SMC may recommend to end the enrollment in the expansion cohort due to safety concerns.

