9.4.4 Sequence of Analyses

This is an exploratory study.

The SMC will review available data during study conduct. The cut off for dose escalation assessments in Part A by the SMC will be triggered by the completion of the DLT period (or discontinuation) of the last participant in the respective dose escalation cohort. If enrollment of the last participant in a dosing cohort is delayed, the SMC may decide on available data for enrollment and dose of the next dosing cohort before all participants in a cohort have completed Cycle 1. In these cases, cut-off can be earlier (after DLT period of the first 2 participants is finished or they experienced a DLT).

For Part A, the cut off for an exploratory interim analysis of the safety, available PK, available Pd and preliminary antitumor activity data from the complete dose escalation will be triggered when all participants enrolled in the dose escalation:

- Had the first on-study intervention tumor assessment or
- Experienced death or
- Withdraw for any reason

whichever comes first.

In Part B, an interim analysis will be conducted after 15 participants who are treated at the same dose are evaluable for response. If at this interim analysis, the dose is increased, one additional interim analysis may occur after 15 participants are treated on the new dose and are evaluable for response. Additionally, there are SMCs planned after 3, 6, and in the following every 6 participants have finished the DLT period. For all SMCs the analyses necessary for these SMCs will be conducted (as described in the integrated analysis plan for SMCs).

Additional analysis during the study might be conducted, e.g., for publication purposes.

The primary analysis will be performed once all participants have completed the second response evaluation (or discontinued prematurely).

Follow-Up analyses to further efficacy and safety data will be done once the End of Study has been reached.

The preliminary food effect will be evaluated at the time of interim analysis in the available participants in Part B. The results will be indicative of whether to evaluate further participants on food effect or stop the food effect evaluation.

More details will be described in the Integrated Analysis Plan.

10 Safety Monitoring Committee

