Unless otherwise stated the calculation of proportions will be based on the number of participants in the analysis set of interest. Therefore, counts of missing observations will be included in the denominator and presented as a separate category.

Deviations from this definition might apply to the PK analysis (see section 16.1 for definitions).

Descriptive statistics will be computed by treatment day (C1D1, C1D2, C1D8, ..., EOT). Unscheduled visits will be included in the derivation of baseline (if occurred within the allowed screening period) or worst on-treatment values and in any analysis using treatment day (e.g. plots of lab data).

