- Number of dosing days (in days) as defined by (date of last dose of study drug–date of first dose of study drug–sum of days with dose interruption +1)
- Total number of cycles received at least 80% of planned dose as defined sum of cycles with received dose \geq 80% of planned dose
- Number and percentage of participants with at least one dose reduction will be presented.

A listing will be provided for all administrations of participants (date and dose of administration) including planned regimen and dose.

14**Efficacy Analyses**

The following analyses will be performed based on the SAF analysis set, by regimen and dose (in increasing order) and summarized. In case the received cumulative dose of a participant is higher than planned cumulative dose the participant will not be considered in efficacy analyses.

14.1**Overall Response**

Overall response (OR) will be assessed based on reported overall responses at different evaluation time points from the treatment start date in accordance to IMWG response criteria, taking requirements for confirmation into account as detailed below.

OR is defined as a confirmed (2 consecutive assessments made at any time before the institution of any new therapy) Best Overall Response of sCR, CR, VGPR, or PR according to IMWG response criteria.

Participants will be considered evaluable for response in the analysis set if they have at least two on-treatment assessment of IMWG response criteria other than Not Evaluable (NE).

Except for participants who have at least one on-treatment assessment of IMWG response criteria and who receive anti-tumor treatments other than the study treatment, die, progress or withdraw for any reason prior to reaching confirmed sCR, CR, VGPR or PR. These will be considered as non-responders in the assessment of OR.

Each evaluable participant will have an objective response status (0: 'no OR'; 1: 'OR') The participants who are not evaluable will be considered Not Evaluable (NE).

OR rate (ORR) is the proportion of participants with OR in the participants evaluable for response in the analysis set.

The ORR by regimen and dose and in summary will be calculated along with the two-sided 95% CI using the Clopper-Pearson method (exact CI for a binomial proportion as computed by default by the SAS FREQ procedure using the EXACT option).

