A table will display the number and percentage of participants evaluable for response, the participants with overall response, including the confirmed IMWG response criteria

Moreover, this descriptive table will include each category of Best Overall Response (sCR, CR, VGPR, PR, MR, SD, PD, NE) according the confirmed and not confirmed IMWG response criteria.

A listing will be also be provided with all IMWG assessments, specifying also the indicators for progressive disease and indicators for clinical relapse, as collected in the CRF.

14.2**Duration of treatment**

A duration of treatment plot by actual time grouped by dose level will be plotted. The plot will be in increasing order of drug intensity (10mg QD at the bottom, the 10mg BIW in the middle and the 20mg BIW at the top) Tumor assessments will be displayed with outcome (e.g. PD or SD)

Molecular information on cytogenetic abnormality (if available) will be specified at the end of each bar.

An arrow at the end of the bar plot will identify the patient with treatment ongoing at the data cut off.

The sCR and CR will be grouped and NE not presented.

14.3**M-protein and FLC**

Serum and urine M-protein (in g/dL and mg/24h respectively) and FLC ratio and FLC values (kappa and lambda) will be listed for all cycles. Changes from baseline will be added to the listing

In all further analysis the affected light chain only will be considered (as per “type of light chain” from eCRF, or if information not available, light chain type with $> 10\text{mg/L} = 1\text{mg/dL}$ at baseline)

The values for serum and urine mprotein, FLC ratio and affected light chain will be summarized using descriptive statistics of relative changes from baseline for each cycle. End of treatment visit will be summarized separately.

Figures

The following graphics will be plotted:

- A waterfall plot depicting the best % change from baseline between serum M-protein, urine M-protein and affected free light chain. Only the best change from the three different biomarkers will be depicted. Displays of serum M-protein will be identified by a circle, the urine M-protein by a triangle, the affected free light chain by a cross. The bar plot will be filled with different color depending of the dose level. If available, filled boxes below the waterfall plot will signify whether a high cytogenetic abnormality (del(17p), t (4;14) t (14;16)) was detected in the patient. Subject ID will be available below the bars.

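### SAP 14 contradicts SAP 7 and 9 on showing over-dosed participants in individual efficacy displays; its ORR leaves unassessed participants out and its waterfall sets no baseline-measurability condition

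*SAP*

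**What the plan says.** SAP 14 analyses efficacy on the safety analysis set (SAF), by regimen and dose. Three of its rules matter here.

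- **Over-dosed participants.** The lead-in to SAP 14 says: "In case the received cumulative dose of a participant is higher than planned cumulative dose the participant will not be considered in efficacy analyses". SAP 7 and SAP 9 treat the same participant differently. They leave the participant out of summary analyses but require the data in efficacy listings and figures at individual level, with a footnote giving the cumulative dose received.
- **Overall response rate (ORR).** SAP 14.1 says: "Participants will be considered evaluable for response in the analysis set if they have at least two on-treatment assessment of IMWG response criteria", not counting those graded Not Evaluable (NE). A participant with at least one such assessment who then dies, progresses, withdraws or starts other anti-tumour treatment before a confirmed response is kept as a non-responder. Anyone else short of two is NE. SAP 14.1 then adds: "OR rate (ORR) is the proportion of participants with OR in the participants evaluable for response in the analysis set". The interval is two-sided 95% Clopper-Pearson. The general default in SAP 9 is: "Unless otherwise stated the calculation of proportions will be based on the number of participants in the analysis set of interest". Missing observations count in that denominator.
- **Waterfall.** SAP 14.3 draws one bar per participant, the best percentage change among serum M-protein, urine M-protein and affected free light chain (FLC). A symbol shows which marker is plotted. No baseline level is required. Spider plots follow for serum M-protein and affected FLC, but not for urine M-protein.

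**The concern.** SAP 5 says Part B will not be done, so these outputs are the trial's only report of clinical activity, in very small groups.

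The over-dose rules cannot all be followed. A programmer working from SAP 14 would drop the participant everywhere; one working from SAP 9 would show and footnote the participant.

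The ORR rule removes the treated participant who was never assessed, even when the reason was early death or withdrawal, because the non-responder exception needs at least one assessment. In a small group, one such participant changes the displayed rate or its upper limit.

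The waterfall can plot a marker that was never measurable disease and show a fall for a participant who meets the criterion for progression on another marker.

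**Working it through.** **Over-dosed participants: the sections side by side.** SAP 7, SAP 9 and SAP 14 agree on exclusion from summaries. They differ on individual displays, and SAP 14 contains six of these: the response-assessment listing, the duration-of-treatment plot, the M-protein/FLC listing, the waterfall and two spider plots. No tolerance is stated, so any excess triggers the rule. In a 28-day Cycle 1, one extra dose at 10 mg once daily gives 290 mg against 10 × 28 = 280 mg (290/280 − 1 = 3.6%). One extra dose at 10 mg twice weekly gives 90 mg against 10 × 8 = 80 mg (90/80 − 1 = 12.5%).

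**ORR denominator.** The plan states no figure for the Part A ORR, so there is none to reproduce.

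Let N be the SAF participants kept in the summaries, E the evaluable ones and r the responders. A confirmed response needs two consecutive assessments, so every responder is evaluable. Hence r/E ≥ r/N, and the gap is r(N − E)/(N·E).

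Final group sizes are not in the documents. SAP 14.2 names three groups ("10mg QD at the bottom, the 10mg BIW in the middle and the 20mg BIW at the top"). Protocol 9.2 says: "The planned cohort size is 3 participants at a given dose", rising to at most 4. I assume groups of 3 or 4, hence 9 to 12 overall, with one participant unassessed. A group of 6 is added for comparison.

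| Setting | NE counted as non-response, r/N (95% CI) | Evaluable only, r/E (95% CI) |
|---|---|---|
| Group of 3, one responder | 1/3 = 33.3% (0.8 to 90.6) | 1/2 = 50.0% (1.3 to 98.7) |
| Group of 4, one responder | 1/4 = 25.0% (0.6 to 80.6) | 1/3 = 33.3% (0.8 to 90.6) |
| Group of 6, one responder | 1/6 = 16.7% (0.4 to 64.1) | 1/5 = 20.0% (0.5 to 71.6) |
| Pooled 9, one responder | 1/9 = 11.1% (0.3 to 48.2) | 1/8 = 12.5% (0.3 to 52.7) |
| Pooled 12, one responder | 1/12 = 8.3% (0.2 to 38.5) | 1/11 = 9.1% (0.2 to 41.3) |

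With no responders only the upper limit moves. For 0/n it is 1 − 0.025^(1/n): 70.8% (0/3) becomes 84.2% (0/2), and 60.2% (0/4) becomes 70.8% (0/3).

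**Waterfall.** Protocol Section 5 needs only one measurable marker at entry: in general, serum M-protein of at least 1.0 g/dL or urine M-protein of at least 200 mg/24 h. Protocol Table 16 calls progression on a 25% rise in any one marker, with an absolute rise of at least 0.5 g/dL for serum M-protein. Illustrative values:

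- Serum M-protein from 2.0 to 2.6 g/dL: 2.6/2.0 − 1 = +30%, absolute rise 0.6 g/dL. This meets the progression rise, if confirmed.
- Urine M-protein from 50 to 30 mg/24 h, below the 200 mg/24 h threshold: 30/50 − 1 = −40%.

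The plotted bar is −40%.

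**The case against.** The evaluable denominator is an explicit definition. Protocol 9.4.1 and SAP 9 both let the plan specify one. The SAP 14.1 table reports the number and percentage evaluable and an NE category, so a reader can recover the other rate. That stands, and a reader who inferred a breach of the SAP's own rules would be wrong.

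Few participants should be affected. The on-treatment period runs to 30 days after the end of intervention (SAP 9.4), and participants who stop treatment complete an End of Study Intervention visit (Protocol 4.1). The primary analysis also waits for everyone's second response evaluation or early discontinuation (Protocol 9.4.4). This narrows the gap without closing it: a participant who dies or withdraws consent before any assessment still leaves the denominator.

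It is tempting to say that the displayed ORR can never fall below the rate in all treated participants. The documents do not support that, because over-dosed participants leave the summaries, responders included. If 9 are treated and the only responder is over-dosed, the display is 0/8 = 0% against 1/9 = 11.1%. The inequality holds only among participants kept in the summaries.

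The SAP 14 over-dose sentence names no listings or figures and could be meant for summaries only. But it is unqualified, and it opens a section made largely of individual displays. A reader might also think no period is given for judging excess dose. The general rule in SAP 9 is set over the DLT period and covers the over-dose case; SAP 14 merely does not repeat it.

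A reader might conclude that the waterfall conceals progression. It does not: the serum rise appears in the serum spider plot, outcomes are marked on the duration plot, the listings carry the values, and each marker is also summarised separately by cycle. FLC is rarely the problem, since serial serum FLC is collected only in free light chain disease (Protocol 8.1 and the Schedules of Activities). What remains is mainly sub-threshold urine M-protein. The documents give no marker variability, so they cannot show how far measurement noise alone would move the bars.

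**Conclusion.** The point holds, as a matter of descriptive secondary reporting. Protocol 9.1 and 9.4 make the study exploratory and descriptive, and no formal decision depends on these outputs.

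- **Over-dose sentence in SAP 14:** wrong as written. Followed literally, it removes participants from displays that SAP 7 and SAP 9 require.
- **ORR denominator:** permitted and disclosed, but improvable at little cost. With one unassessed participant and one responder, the shift is about 8 to 17 percentage points in a group of 3 or 4, and about 1 point pooled over 9 to 12. Group sizes and the unassessed count are assumptions.
- **Waterfall:** also improvable at little cost. The bar can contradict a participant's progression status, though other outputs reveal the rise. How often this would happen cannot be worked out from the documents.

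**What to change.** 1. **Over-dose sentence.** Reword SAP 14 so that these participants are left out of efficacy summaries only and appear, footnoted, in individual listings and figures. State that excess dose is judged over the DLT period, as in the SAP 9 general rule.
2. **ORR.** Report it with its Clopper-Pearson interval over SAF participants by planned dose, counting NE as non-response. Apply the same over-dose exclusion as the other summaries and say so in a footnote. Keep the evaluable-only rate as supportive.
3. **Waterfall.** Restrict it to markers meeting the Protocol Section 5 threshold at baseline, and use FLC only when serum and urine M-protein are not measurable, as in Protocol Table 16. Add a urine M-protein spider plot.

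The cost is SAP wording, minor reprogramming and one extra figure, with no new data. The ORR and the waterfall may look slightly less favourable. Where serum and urine M-protein are both measurable, the bar remains the better of the two, but the spider plots would then show both.

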15.1 DLT analysis

Of Note, DLT as per SMC decision will be available in the table “Review of data” in the SMC minutes.

In case of new DLT appears after DLT period, the minutes will be updated.

A table will display the following (per regimen and dose level and in total) for the DLT analysis set:

- Number and percentage of participants with a DLT per investigator's judgement as recorded in eCRF (using DLT flag from the AE CRF page)

Number and percentage of participants with a DLT per SMC decision

A listing of DLTs (per investigator and/or per SMC) will be provided by dose level and participant, including whether it was judged to be a DLT by investigator and/or by SMC

This listing will additionally contain age, sex, type of myeloma, SOC, PT, grade, SAE (yes/no), relatedness to M3258 (yes/no), start date (+treatment day), stop date (+treatment day), action taken with M3258, if treatment was stopped before start of AE: days since stop of treatment, and outcome.

In addition, the following will be presented:

- Quantiles (2.5%, 25%, 50%, 75% and 97.5%) for the posterior probability of a participant experiencing a DLT at each of the dose levels used in the study according to the same Bayesian Logistic Model (BLM) as described in the SMC IAP (see [Appendix 18.1](#)) or

SMC charter (if change occurred). For this analysis either SAS or R (using the package bcrm or crmPack) will be used.

MTD suggestion from the Bayesian logistic regression model

The MTD as suggested from the modeling will be derived as follows:

- 1) The BLRM will be updated with all DLT data (SMC decision) from the dose escalation.
- 2) The dose with targeted toxicity probability of 25% will be identified.
- 3) The next lower tested dose with the upper bound of the 95% credible interval of a potential MTD below or equal 40% and with estimated DLT probability above or equal to 17% will be selected.
- 4) The credibility interval will be provided.
- 5) If the MTD estimate of all tested doses is below 17%, there is no MTD suggestion from the model.

This information will be forwarded to the SMC that will decide on the determination of the MTD.

Additionally, the SMC will receive the estimated DLT probability and associated probability quantiles for all other doses tested.

For above analysis either SAS or R (using the package bcrm or crmPack) will be used.

Frequentist MTD suggestion

As second approach, the MTD as suggested by the frequentist estimation will also be derived:

- 1) All DLT data from the dose escalation will be included in a two-parameter logistic regression model (intercept and slope over log of the scaled dose, no prior; if the model does not converge, it will be reported as not calculable; the program code for this analysis can be found in the TLF shells).
- 2) The dose with targeted toxicity probability of 25% will be identified.
- 3) The next lower tested dose will be selected.

The two-sided confidence interval for the DLT probability will be provided.

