Prior median	8%	13%	18%	22%

DLT = Dose-limiting toxicity.

Details of the model, including the prior distribution can be found in [Appendix 10](#).

Decisions of the SMC in the expansion cohort will also be aided by a Bayesian two-parameter logistic regression model with the same specifications as for the dose escalation, except the prior. The prior will be based on the data seen in the monotherapy dose escalation and specified in the SMC charter before the first SMC for the expansion cohort occurs. The model will be updated at times of SMCs in the expansion cohort. Additional stopping rules in Part B apply (see Section [7.1](#)).

Other specifications are as for dose escalation and can be found in [Appendix 10](#).

Details on analyses for SMCs will be described in the SMC Integrated Analysis Plan.

All other safety analyses will be performed on the Safety Analysis population.

Endpoint	Statistical Analysis Methods
Primary (DLTs)	After end of dose escalation and main analysis, the number and proportion of participants experiencing DLTs will be reported by dose level, based on observations during the first study intervention cycle. Posterior probabilities (2.5%, 25%, 50%, 75%, and 97.5% quantiles) for DLT probabilities at selected doses will be estimated from the Bayesian logistic regression model. A sensitivity analysis will be performed using frequentist modeling (without prior).
Secondary	In general, continuous variables will be summarized using number of participants (n); mean, standard deviation; median, 25 th Percentile to 75 th Percentile (Q1-Q3), minimum, and maximum. If there are less than 5 observations available only mean and the observed data will be given. Categorical variables will be summarized using frequency counts and percentages. The calculation of proportions will be based on the number of participants in the analysis set of interest, unless otherwise specified in the study Integrated Analysis Plan. Details will be specified in the Integrated Analysis Plan finalized before database lock.
Tertiary/Exploratory	Details will be specified in the Integrated Analysis Plan finalized before database lock.

DLT = Dose-limiting toxicity.

QT/QTc Analysis

The ECG parameter will be summarized by descriptive statistics per time point; changes from Baseline will be calculated.

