In case information arises from other studies that changes current knowledge on the dose toxicity relationship, the prior distribution can be updated prior to the first participant being treated in this study. If a change in regimen occurs, a separate model will be set up for each regimen. Any change in prior and the priors for changed regimens will be documented in the SMC charter.

Decisions of the SMC in the expansion cohort will also be aided by a Bayesian two-parameter logistic regression model with the same specifications as for the dose escalation, except the prior. The prior will be based on the data seen in the dose escalation and be specified in the SMC charter. The model will be updated at times of SMCs in the expansion cohort.

Posterior distribution and the recommended next dose level suggested by the model will be calculated using EAST version 6.4 or higher/ R version 3.4.2 or higher with library package bcrm ([Sweeting et al, 2013](#)) or package CRMpack or SAS version 9.4 (or higher) proc MCMC.

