$0 * P(\text{target dosing (estimated DLT rate in (0.2-0.35)}) + 1 * P(\text{under dosing (estimated DLT rate in [0-0.2])}) + 2 * P(\text{for over dosing (estimated DLT rate in (0.35-0.6])}) + 3 * P(\text{excessive dosing (estimated DLT rate in (0.60-1])})$.

The recommended dose level resulting from the model for the next cohort is the dose with the lowest loss function. This Bayesian escalation approach will be used to assist the SMC to select the next dose from a predicted set of acceptable doses, i.e., 10 mg, 20 mg, 35 mg, 50 mg. It is possible to choose a dose(s) not within the pre-specified dose-escalation plan. In this case the estimated posterior probabilities of the selected dose will also be provided to the SMC.

The model will continue to be updated at each SMC until the SMC has decided to stop dose escalation.

Prior distribution and likelihood are used to calculate the posterior probabilities based on Bayes theorem.

The likelihood is defined based on a binomial distribution, modelling the rate of subjects with at least 1 DLT.

The relationship between dose and toxicity rate is defined by

$$P(DLT|d_j, \alpha, \beta) = \frac{\exp\left(\alpha + \exp(\beta) * \log\left(\frac{d_j}{d_{ref}}\right)\right)}{1 + \exp\left(\alpha + \exp(\beta) * \log\left(\frac{d_j}{d_{ref}}\right)\right)}$$

Where $d_j \in \{10 \text{ mg, 20 mg, 35 mg, 50 mg}\}$ (or different) and (α, β) are bivariate normally distributed. Reference dose d_{ref} is 90 mg. The chosen prior for monotherapy escalation has the following parameters

$E(\alpha) = -0.708$,

$E(\beta) = -0.389$,

$SD(\alpha) = 1.2$, $SD(\beta) = 0.9$, $Cov(\alpha, \beta) = 0$.

The prior distribution has not been changed compared to the protocol defined.

CCI

CONFIDENTIAL
INFORMATION

18/38

M3258

First in Human Dose Escalation of M3258 as a Single Agent and Expansion
Study of M3258 in Combination with Dexamethasone

MS201814-0010

Version 2.0

Handling of changes in regimen

For different regimens, separate models will be used. In general, the same specifications outlined above will be used for each of these models, applicable to the dose given on the treatment days, unless otherwise specified. This means that in a once daily (QD) regimen, 90 mg as reference dose refers to the dosing of 90 mg daily. In a twice weekly regimen (on day 1,4,8,11, etc) the 90 mg reference dose refers to a dosing of 90 mg on day 1, day 4 etc. The approach is not considering weekly cumulative dosing.

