Rationale for keeping the same prior: It is assumed that changes in regimen occur due to the fact that the observed dose-toxicity relationship was not as a priori expected. It is further assumed that after the change in regimen the dose- probability of DLT relationship in the new regimen is coming closer to the a priori expected dose-toxicity relationship.

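### As literally written, the frequentist MTD fit in SAP 15.1 puts two dosing regimens on one curve, while the Bayesian model it checks is separate by regimen (minor)

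*SAP*

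**What the plan says.** SAP section 15.1, under the frequentist MTD suggestion, has three steps: fit a model, find the dose with 25% DLT probability, and take the tested dose just below it. For the first step: "All DLT data from the dose escalation will be included in a two-parameter logistic regression model". The bracket that follows gives the terms and the fallback: "intercept and slope over log of the scaled dose, no prior; if the model does not converge, it will be reported as not calculable". It then says that "the program code for this analysis can be found in the TLF shells". Scaled dose is not defined there, and regimen is not mentioned. Protocol section 9.4.2 calls this fit a sensitivity analysis to the Bayesian DLT model and describes it only as frequentist and without a prior.

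The Bayesian model has an explicit regimen rule. Protocol Appendix 10: "If a change in regimen occurs, a separate model will be set up for each regimen". The SMC analysis plan (SAP Appendix 18.1, its section 15.1, on changes in regimen): "For different regimens, separate models will be used". For a twice-weekly regimen that plan adds that "the 90 mg reference dose refers to a dosing of 90 mg on day 1, day 4 etc", so its dose scale is dose per administration, and it says that weekly cumulative dose is not considered. Protocol section 9.4.2 is looser and allows either an extended or a separate model.

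SAP section 14.2 lists the groups for its treatment-duration plot as 10 mg QD, 10 mg BIW and 20 mg BIW.

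**The concern.** A sensitivity analysis that drops the prior should differ from the base analysis in the prior only. As written, this one also drops the split by regimen. It takes up neither option in protocol 9.4.2, because an intercept and a slope are neither separate models nor a model extended for regimen.

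The plan's own reasoning speaks against a common curve. The SMC analysis plan explains why the same prior is kept after a switch: "It is assumed that changes in regimen occur due to the fact that the observed dose-toxicity relationship was not as a priori expected". It then assumes that the relationship in the new regimen comes closer to what was expected, so the curve is taken to differ between regimens.

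Two things are at stake. The fitted rate at 10 mg would be an average of two regimens and describe neither. And the fallback label *not calculable*, which should warn that the data are too thin, could be bypassed: pooling can yield a finite fit, and a printed 10 mg, when neither regimen supports a fit alone.

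**Working it through.** **Plan's own figure.** None exists for this analysis. As a side check on the dose scale, simulating the Bayesian prior (reference dose 90 mg) gave mean DLT rates of 14.7, 18.8, 23.5 and 27.5% at 10, 20, 35 and 50 mg, against 15, 19, 24 and 28% in protocol 9.4.2.

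**Inputs from the documents.** Groups QD10, BIW10 and BIW20 (SAP 14.2); target 25%; planned cohort size 3 (protocol 9.2).

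**Assumptions.** BIW is the protocol's twice-per-week regimen; scaled dose is dose per administration/90 mg; 10 mg is the only QD dose; all DLT rates and counts are assumed; BIW20 has 3 or 6 participants.

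**1. What pooling equates.** Weekly dose is 7 × 10 = 70 mg for QD10, 2 × 10 = 20 mg for BIW10 and 2 × 20 = 40 mg for BIW20. On the per-administration scale the first two are the same dose, and BIW20 ranks above QD10.

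**2. Fitted rate at 10 mg.** The model is logit(p) = a + b·log(dose/90). With two distinct dose values it is saturated, so the fitted rate at 10 mg is the pooled proportion. With equal group sizes its expectation is (pQD + pBIW)/2, and it misses each regimen by (pQD − pBIW)/2.

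**3. When a fit is calculable.** A finite maximum likelihood estimate needs 0 < x < n at every distinct dose. QD alone has one dose, so two parameters can never be estimated. With 3 participants per 10 mg group and n at BIW20, the probability that the pooled fit is calculable and the BIW fit is not is

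[1 − (1−pQD)³(1−pBIW)³ − pQD³·pBIW³ − (1 − (1−pBIW)³ − pBIW³)] × [1 − (1−p20)ⁿ − p20ⁿ].

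For 20/10/20% and n = 3: (1 − 0.373 − 0.000 − 0.270) × 0.480 = 0.171.

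| Assumed QD10 / BIW10 / BIW20 | Expected 10 mg rate | Miss per regimen (points) | Pooled only, n = 3 | Pooled only, n = 6 |
|---|---|---|---|---|
| 50 / 5 / 15% | 27.5% | 22.5 | 28.7% | 46.7% |
| 40 / 5 / 15% | 22.5% | 17.5 | 25.7% | 41.9% |
| 50 / 10 / 20% | 30.0% | 20.0 | 30.7% | 47.1% |
| 33 / 10 / 25% | 21.5% | 11.5 | 28.7% | 42.0% |
| 50 / 10 / 25% | 30.0% | 20.0 | 35.9% | 52.5% |
| 20 / 10 / 20% | 15.0% | 5.0 | 17.1% | 26.3% |

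**4. When a dose is printed.** The 25% dose is 90·exp[(logit 0.25 − a)/b]. In the first five rows, the pooled fit alone is calculable and a tested dose lies below the 25% dose in 15.8 to 28.5% of trials. Part of that comes from reversed slopes. Counting positive slopes only, 10 mg is printed in 7.2 to 18.2%. The BIW fit is calculable in only 5.5 to 22.2% of trials.

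**5. Example.** QD10 1/3, BIW10 0/3, BIW20 1/3. Pooled: 1/6 = 17% at 10 mg and 1/3 = 33% at 20 mg. The slope is (logit 0.333 − logit 0.167)/log 2 = (−0.693 + 1.609)/0.693 = 1.322, the intercept 1.295 and the 25% dose 14.7 mg, so 10 mg is printed. By regimen, neither fit is calculable. The exact 95% intervals are 0.8–90.6%, 0–70.8% and 0.8–90.6%.

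**6. The opposite direction.** QD10 3/6, BIW10 1/6, BIW20 2/6. Pooled: 4/12 and 2/6, both 33%, so the slope is 0 and no dose has 25%. BIW alone gives 14.7 mg and hence 10 mg.

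**The case against.** The strongest reply is that silence about regimen is not an instruction to pool. The Bayesian step in the same section also feeds all escalation DLT data into the model without mentioning regimen, yet that model is separate by regimen. An analysis defined only by removing the prior would ordinarily keep the rest of the base model. SAP section 9 has results displayed separately by regimen, the DLT count table is per regimen and dose level, and the code sits in TLF shells that are not among the documents. A reader might infer that the trial will in fact pool the regimens, or that the Bayesian derivation is pooled too. The documents support neither. Actual pooling cannot be shown without the code, and SAP 15.1 takes its Bayesian model from the SMC analysis plan, which carries the regimen rule.

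What remains is the text of the frequentist step. It names its data and both of its parameters, and it cites no model with a regimen rule. Section 9 governs display, not fitting. Followed as written, it gives one curve.

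The reply also has force on size. Five of the six rate sets assume a wide gap between QD and BIW. With 20% against 10% the miss is 5 points and the pooled-only share 17 to 26%. And much of the printed-dose figure with 6 participants at BIW20 reflects reversed slopes, which fitting by regimen does not cure: for 50/5/15% it is 26.2% in all but 7.2% with a positive slope.

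**Conclusion.** The point holds as a defect in the written specification, at minor severity and with medium confidence. Read literally, SAP 15.1 specifies one model over two regimens, against the by-regimen rule for the model it checks. If scaled dose is dose per administration, 10 mg QD and 10 mg BIW share one DLT probability and the output need not identify a regimen. Under the assumed rates, the fitted 10 mg rate misses each regimen by about 5 points (20% against 10%) to 22.5 points (50% against 5%), and the pooled fit alone is calculable in about 17 to 53% of trials. These figures illustrate the mechanism; they do not predict this trial's result.

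The consequence is limited. All analyses are descriptive, the trial stopped before Part A met its primary objective (SAP section 7), DLT counts by regimen and dose are already planned, and the SMC decides the MTD. The gap may be a drafting omission that the code already avoids.

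**What to change.** In SAP 15.1:

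- State that the frequentist MTD derivation and, for clarity, the Bayesian one are run separately by regimen on that regimen's DLT data, as in protocol Appendix 10 and the SMC analysis plan. Of the two options in protocol 9.4.2, this takes the separate model.
- Define scaled dose as dose per administration divided by 90 mg. The constant does not alter fitted probabilities; the words *per administration* settle the scale.
- Where a regimen has one tested dose or no finite estimate, report *not calculable* and show x/n with an exact 95% interval.
- Label any MTD suggestion with its regimen, and give none across regimens.

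The cost is a sentence or two and a by-regimen model call, with no new data. If the TLF-shell code already fits by regimen, only the wording changes. The drawback is that the frequentist result will often be *not calculable*: always for QD if 10 mg is its only dose, and in roughly 78 to 95% of trials for BIW under the assumed rates (100 minus 22.2, and 100 minus 5.5). With so few participants, that is the honest output.
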